3. STUDY DESIGN

3.1. Overall Design

This Phase 2 randomized, double-blind, multi-center study will evaluate the efficacy, safety, and PK of etrasimod compared with placebo for 24 weeks in adults with active EoE.

The study will consist of a Screening Period of up to 35 days, 24 weeks of double-blind treatment (Double-Blind Treatment Period), 28 weeks of active extended treatment (Extension Treatment Period), and 4 weeks of follow-up (Safety Follow-Up Period) for a total study duration of up to 61 weeks.

Eligible subjects will be randomized in a double-blinded fashion (3:3:2 ratio) to etrasimod 1 mg, etrasimod 2 mg, or matching placebo once daily. Randomization will be stratified by baseline history of esophageal dilation (yes/no) and concurrent PPI therapy (yes/no).

[figure not shown]
All subjects who complete the Double-Blind Treatment Period and meet eligibility criteria for the Extension Treatment Period may enter the Extension Treatment Period.

Subjects who were in etrasimod 1 mg or etrasimod 2 mg groups in the Double-Blind Treatment Period will continue the same etrasimod dose in the Extension Treatment Period. Subjects who were in the placebo group during the Double-Blind Treatment Period will be re-randomized (1:1 ratio) to etrasimod 1 mg or etrasimod 2 mg at entry into the Extension Treatment Period.

Subjects will have follow-up visits at 2 and 4 weeks after the last dose of study treatment after Week 52 or the Early Termination (ET) Visit.

A study design schematic is shown in [Figure 1](#).

Figure 1: Study Design

*Esophagogastroduodenoscopy
 EoE, eosinophilic esophagitis; ETR, etrasimod; F/U, follow-up; PBO, placebo.
 Numbers preceded by colons represent the randomization ratio.

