4. STUDY POPULATION

4.1. Inclusion Criteria

Subjects must meet ALL the following inclusion criteria to be eligible for enrollment into the study.

1. Men or women between 18 to 65 years of age at the time of informed consent (IC)
2. Provide signed IC and willing to comply with all protocol-specified assessments and procedures
3. Have an EoE diagnosis prior to screening and histologically active disease with an esophageal PEC of ≥ 15 eos/hpf (~ 60 eos/mm²) from any level (proximal, mid, or distal) of the esophagus at the Screening EGD.
4. Have dysphagia, defined as solid food going down slowly or getting stuck in the throat with an average frequency of ≥ 2 episodes per week over 2 weeks (as documented using the DSQ during the Screening period)

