9.2. Screening

Subjects must sign the informed consent form (ICF) and meet study eligibility criteria before any study-specific procedure can be performed ([Section 12.2](#)).

All screening evaluations should be completed and reviewed within 35 days prior to Day 1 to confirm subject eligibility. In some cases, the screening visit window for a given subject may be extended by 2 business days beyond the date the Investigator receives the screening histopathology report to confirm subject eligibility. Note that only extension of the screening visit window due to a legitimate delay in the reporting of screening histopathology report will be approved by the Medical Monitor and will not be considered a protocol deviation.

Refer to [Appendix 11](#) for modification in the event that COVID-19 or similar PHE-related restrictions limit the capacity to perform certain Screening assessments.

The Medical Monitor should be consulted to see whether repeat testing is needed if the subject is planned to be enrolled > 35 days from the signing of the ICF.

The Screening EGD should be performed early in the screening period (preferably within the first 7 days of the screening period) to allow sufficient time for central reading to confirm eligibility by histology.

During Screening, subjects will record daily presence of dysphagia to solid food in their eDiary, according to the question-answer format of the DSQ. Subjects will begin daily eDiary entries starting on the first day of Screening after the eDiary training is completed. eDiary device and training should be provided at Screening to ensure capturing of entries within the required 14-day period. Study site staff will monitor the eDiary compliance. At least 8 DSQ daily entries in the last 2 weeks prior to Day 1 visit as well as completion of Patient Global Impression of Severity (PGIS) are needed for randomization.

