10.4.3.1. Dysphagia Symptom Questionnaire

The DSQ is a validated patient-reported outcome questionnaire that captures the presence and severity of dysphagia to solid food in patients with EoE. Subjects record whether they have eaten solid food since waking up, any dysphagia to solid food on that day, dysphagia severity based on relief strategies utilized during the dysphagia episode and the severity of the worst daily pain related to swallowing, if there is any [47,53]. The DSQ will be used to characterize baseline dysphagia severity and changes with treatment intervention.

Questions 1 and 2 of the DSQ from the subject's daily eDiary entries will be used to determine the eligibility regarding active dysphagia during the Screening Period. One episode of dysphagia is counted when a subject responds "yes" to questions 1 and 2 of the DSQ. Subjects must have at least an average of 2 episodes of dysphagia per week over 2 weeks during the Screening Period.

During the study, the DSQ will be completed daily in the evening after the last meal of the day.

The DSQ will be scored over a 14-day period, and a minimum of 8 DSQ daily eDiary entries out of the 14-day period preceding the date of scoring are required to calculate DSQ score. The DSQ total score range is 0 to 84.

Daily dysphagia symptom diary questions are provided in [Appendix 4](#).

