5.6. MODIFIED FULL ANALYSIS SET

The modified FAS (mFAS) will consist of all randomized subjects who receive at least 1 dose of study treatment in the Double-Blind Treatment Period and have a Baseline and at least 1 post-randomization measurement. In addition, subjects with baseline DSQ total score <8 will be excluded from mFAS for DSQ based endpoint analyses. Subjects will be summarized by treatment to which they were randomized, regardless of treatment actually received. Note that the mFAS can vary with endpoints since some subjects may have the needed data for inclusion in the mFAS for some endpoints, but not for other endpoints.

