17.2.1. SECONDARY EFFICACY VARIABLES & DERIVATIONS

The secondary efficacy analyses will be performed for the FAS. The secondary efficacy endpoints are:

- Change from Baseline in DSQ total score at Week 16
- Change from Baseline in Esophageal PEC at Week 16.
- Proportion of Subjects with Esophageal PEC < 15 eos/hpf at Week 16
- Proportion of Subjects with Esophageal PEC \leq 6 eos/hpf at Week 16

Change from Baseline in DSQ total score at Week 16 will be based on daily DSQ score from subject daily Diary data. The DSQ total score and daily DSQ score calculations are provided below. An increase in DSQ total score indicates worsening of dysphagia symptoms.

Calculation Approach	DSQ Total Score	Daily DSQ Score
14-day period approach ^a	
DSQ total Score = (Sum of daily DSQ score with 14-day period preceding the scheduled visit day) \times 14 / (Number of days with diaries reported with nonmissing data within 14-day period).
 
Shifting rule when calculating DSQ total score at each visit based on the number of reported diary entries within the 14-day period prior to the visit:
 
Baseline visit :
 
If there are less than 8 reported diaries that are available within the 14-day period prior to baseline, then the most recent 8 reported diaries in a consecutive 14-day period would be used to calculate the DSQ total core. In order to determine the most recent 14-day period with the minimum number of reported diaries, it may be necessary to make adjustments in some cases by shifting to earlier diary entries. Such 14-day periods cannot be shifted for more than 7 days (not including the study visit day). After shifting 7 days, if there are still less than 8 reported diaries
	
Daily DSQ Score= sum of answers to Questions 2 and 3 in the daily DSQ questionnaire
 
Daily DSQ Score is set to missing if the diary is not reported or if the diary is reported but the answer to Question 1 is “No” in daily DSQ questionnaire. In this case the diary is considered as missing
 
Daily DSQ Score is set to zero if the answer to Question 2 is “No” in daily DSQ questionnaire

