17.2.3. PRIMARY ANALYSIS OF SECONDARY EFFICACY VARIABLES

17.2.3.1. Change from Baseline in DSQ total score and Esophageal PEC at Week 16

Analysis of the secondary efficacy variables change from Baseline in DSQ total score at Week 16 will use a linear mixed effect model. The linear mixed effect model will include treatment group, visit, interaction of treatment-by-visit, Baseline history of esophageal dilation (Yes or No), and concurrent PPI therapy (Yes or No) as factors and Baseline DSQ total score as a covariate using an unstructured covariance matrix. If there is a convergence issue in fitting the unstructured covariance, a compound symmetry covariance structure will be used. The Kenward-Rogers method will be used to estimate the denominator degrees of freedom. Change from Baseline in Esophageal PEC at Week 16 will use an ANCOVA model including treatment group and randomization stratification factors as factors and Baseline eosinophil PEC as a covariate. Eosinophil PEC assessments after rescue medication and/or rescue procedure use will be set to missing. LS means at visit and LS mean differences between treatment groups (i.e. etrasimod 1 mg vs placebo, etrasimod 2 mg vs placebo, and etrasimod pooled vs placebo) with p-values and corresponding 95% CIs will be reported. For the individual etrasimod summaries, treatment group will include placebo, etrasimod 1 mg and etrasimod 2 mg. For the pooled etrasimod summary, treatment group will include placebo and pooled etrasimod.

17.2.3.2. Proportion of Subjects with Esophageal PEC < 15 and ≤ 6 eos/hpf at Week 16

Analysis of the secondary efficacy variables proportion subjects with esophageal PEC < 15 eos/hpf at Week 16 and proportion of subjects with esophageal PEC ≤ 6 eos/hpf at Week 16 will be performed for randomization stratification factors of baseline history of esophageal dilation (Yes or No) and concurrent PPI therapy (Yes or No). Subjects who use rescue medication or have a rescue dilation, or with missing data at Week 16 for any reason will be considered nonresponders. The stratified analyses will be performed for randomization stratification factors. Results will be expressed as the number and percentage of subjects who achieved the goal, risk difference in

CCI [REDACTED]

- | [REDACTED]
- | [REDACTED]
- | [REDACTED]
- | [REDACTED]
- | [REDACTED]
- | [REDACTED]
- | [REDACTED]

CCI [REDACTED]

[REDACTED]

CCI [REDACTED]

CCI [REDACTED]	[REDACTED]	[REDACTED]	[REDACTED]	[REDACTED]

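### The diary count required for randomization includes no-solid-food days that the SAP scores as missing, so a randomized subject can have no baseline DSQ, or one resting on too few days

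*Protocol*

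**What the plan says.** **Diary count.** Protocol 9.2 requires "At least 8 DSQ daily entries in the last 2 weeks prior to Day 1 visit", together with the PGIS, before randomization. The Appendix 1 schedule repeats this. Protocol 10.4.3.1 uses the same unit for scoring: "a minimum of 8 DSQ daily eDiary entries out of the 14-day period preceding the date of scoring are required to calculate DSQ score". None of these places asks whether solid food was eaten.

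**Scoring.** SAP 17.2.1 adds the daily scores, multiplies by 14 and divides by the number of days with nonmissing data. If Question 1 is answered No, the daily score is missing, and "In this case the diary is considered as missing". With fewer than 8 reported diaries in the 14 days before baseline, the window may move back by at most 7 days. If that fails, baseline is set to missing.

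**Eligibility.** Inclusion 4 asks for an "average frequency of ≥ 2 episodes per week over 2 weeks (as documented using the DSQ during the Screening period". Section 10.4.3.1 words it as "Subjects must have at least an average of 2 episodes of dysphagia per week over 2 weeks during the Screening Period". Section 3.1 adds "The study will consist of a Screening Period of up to 35 days", and 9.2 starts the diary on the first screening day, once training is done.

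**Analysis.** SAP 17.2.3.1 analyses change in DSQ with a mixed model that has "Baseline DSQ total score as a covariate using an unstructured covariance matrix". The analysis set is the FAS, meaning all subjects randomized and dosed. A footnote to the SAP's table of planned analyses by endpoint says that no other missing-data method is needed because the model deals with missing data. Only for the mFAS does SAP 5.6 say that "subjects with baseline DSQ total score <8 will be excluded from mFAS for DSQ based endpoint analyses".

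**The concern.** The check before randomization and the rule that computes the baseline count different things. The check counts entries. The scoring uses only entries with solid food, called usable diaries below. The subjects caught between the two are those who avoid solid food, in some cases because of EoE. They are found only after randomization, when the screening diary can no longer be extended.

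A mixed model copes with a missing outcome. It cannot use a subject whose baseline is missing, because neither the change score nor the covariate exists. Such a subject is in the FAS by definition and absent from the FAS analysis in practice.

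The loose eligibility fortnight is a second, smaller gap. A subject may qualify early in screening and be nearly symptom-free in the fortnight that is scored. The score then has little room to fall.

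**Working it through.** **1. Scale.** Question 2 scores 0 or 2 and Question 3 scores 0 to 4, so the daily maximum is 6. Over 14 days, 14 × 6 = 84, which is the stated upper limit.

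**2. A subject who passes and has no sound baseline.** In the last 14 days, take 4 episode days, 4 days with Question 1 = No and 6 days without an entry.
- Entries: 4 + 4 = 8, so the count is met.
- Episodes: 4 in 2 weeks, so Inclusion 4 is met.
- Usable diaries: 4.

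The SAP can be read in two ways.
- *Reading A:* No-days do not count as reported diaries. The window is shifted. If no window within the 7-day limit holds 8 usable diaries, baseline is missing.
- *Reading B:* No-days count as reported. No shift is triggered and the total rests on 4 days. Its minimum is 4 × 2 × 14/4 = 28. The same four episodes over 14 usable days give 4 × 2 × 14/14 = 8. Each usable day stands for 14/4 = 3.5 days.

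**3. Baseline below 8.** With at least 4 episodes in the scored fortnight and n usable days, the minimum is 4 × 2 × 14/n. That is 8 at n = 14 and 14 at n = 8. A baseline below 8 thus requires fewer than 4 episodes in the scored fortnight. Three episodes on 14 usable days with Question 3 = 0 give 3 × 2 = 6. Thirty-five days contain 35 − 14 + 1 = 22 fortnights. A subject can qualify on Days −35 to −22, make 8 or more symptom-free entries on Days −14 to −1 and have a baseline of 0.

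**4. Frequency under assumptions.** The documents give no rates, so all of these are assumed: independent days; diary completion 75% or 90%; solid food on 70%, 80% or 90% of days; dysphagia on 35% of solid-food days; 21 to 35 diary days; any screening fortnight may qualify. I simulated 300,000 subjects per cell. The last two columns are among subjects who meet both Inclusion 4 and the diary count; their ranges run from 21 to 35 diary days.

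| Completion | Solid food | Baseline missing after shift (A), diary count only | Baseline missing after shift (A) | Fewer than 8 usable days in last 14 (B) |
|---|---|---|---|---|
| 75% | 70% | 28% | 14-22% | 37-46% |
| 75% | 80% | 10% | 5-8% | 20-25% |
| 75% | 90% | 2% | 1-2% | 7-9% |
| 90% | 70% | 8% | 3-6% | 16-21% |
| 90% | 80% | 1% | 0.5-1% | 4-6% |
| 90% | 90% | <0.1% | <0.1% | 0.6-0.8% |

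The third column ignores Inclusion 4, which itself requires solid-food days with symptoms, and so overstates the problem. The fourth is the relevant one under Reading A: about 0 to 22%.

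**The case against.** **The SAP may not require 8 usable diaries.** It separates reported from nonmissing, and its Appendix 3 repeats the protocol's unit of daily entries. Under Reading B a missing baseline is practically excluded. This stands as an ambiguity and limits the claim: one cannot say flatly that these subjects have no baseline. Reading B does not remove the problem, though, because the score then rests on fewer than 8 days.

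**Other analyses help.** The worst-case score gives 6 to days without solid food because of EoE symptoms, so those days become scored. Multiple imputation and a tipping-point analysis are listed for DSQ, and the mFAS removes baselines below 8. These reduce the effect. But they are sensitivity or supplementary analyses, imputation of a missing baseline is not specified, and days avoided for other reasons stay missing.

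**The fortnight may be meant as one fixed period.** Section 9.2 mentions a required 14-day period, and the mFAS cut-off would also catch subjects enrolled in breach of Inclusion 4. Both are possible. Still, only the entry count is tied to the last 2 weeks.

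**A stronger reading to avoid.** A reader might infer that the loose eligibility fortnight inflates regression to the mean. It is the reverse. With independent days and no treatment effect, a subject with a true rate of 1.5 episodes per week shows a mean spontaneous change of −1.7 episodes per fortnight if qualified on the baseline fortnight. If any fortnight may qualify, the change is −0.5 (28 days) or −0.3 (35 days). At 2 per week the figures are −1.1 versus −0.2 or −0.1. The effect is the same in all arms, and Protocol 3.2 gives it as a reason for the placebo control.

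**Stakes.** PEC, the primary endpoint, is unaffected, and p-values are unadjusted in this phase 2 study.

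**Conclusion.** The mismatch of units holds. The randomization check and the protocol's scoring minimum accept entries that the SAP treats as missing, so a randomized subject can have no baseline DSQ or one based on fewer than 8 usable days. With no baseline, the subject leaves the FAS mixed model, and the footnote that relies on that model does not cover this case.

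It also holds that baseline DSQ can fall below 8, because eligibility and scoring need not use the same fortnight. The exclusion of such subjects applies to the mFAS, whereas the main DSQ analysis uses the FAS.

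The size is open. About 0 to 22% without a baseline is a range under assumed rates, not an estimate for this trial. A reader might infer a loss as high as 28%, but that figure leaves out Inclusion 4. The sample is small, about 96 subjects with 96 × 2/8 = 24 on placebo, so even 5% would be about 5 subjects. The correction is cheap and worth making. Aligning the eligibility fortnight as well is a trade-off, not a clear gain.

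**What to change.** **Wording.** In Protocol 9.2, 10.4.3.1 and the Appendix 1 schedule, define the minimum as 8 diaries with Question 1 = Yes in the 14 days before Day 1, and program it in the eDiary eligibility report. In SAP 17.2.1, state that 'reported diaries' means these diaries, and use the same unit in SAP Appendix 3.

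**If enrolment is complete.**
- List by arm the subjects with a missing baseline DSQ and those with baseline below 8.
- Keep subjects with a missing baseline in the FAS DSQ analysis by multiple imputation of the baseline, and specify the imputation model before unblinding.
- Repeat the Week 16 DSQ analysis without subjects whose baseline is below 8.

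**Cost.** No new assessment is needed. Some candidates who avoid solid food would need more diary days or the rescreening that Protocol 10.3.7 already allows, or would not be randomized.

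**Optional.** Judging the episode criterion on the same 14 days would guarantee a baseline of at least 8. If this is chosen, the plan should name the price: more regression to the mean, as shown above, and a lower pass rate. For a subject at exactly 2 episodes per week, in the same independent-days model, 60% would qualify, against 90% (28 days) or 95% (35 days) if any fortnight may qualify.

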9.3. Double-Blind Treatment Period

9.3.1. Day 1 Pre-Randomization and Predose

The day of administration of the first dose is defined as Day 1.

The following procedures/assessments must be performed and assessed again on Day 1 to confirm eligibility before randomization:

- HR and BP, followed by 12-lead ECG
- Pregnancy test for all WOCBP

If the subject remains eligible based on HR, BP, and 12-lead ECG parameters, and has a negative pregnancy test result (WOCBP only), then blood samples for laboratory and PK assessments will be collected, after the 12-lead ECG assessment is completed.

Subjects will also complete selected questionnaires to assess baseline status.

9.3.2. Day 1 Randomization and Postdose

After the eligibility criteria have been confirmed and the Day 1 predose assessments (Section 9.3.1) are completed, subjects will be enrolled and randomly assigned to treatment.

First dosing of study treatment will be given, and cardiac monitoring will take place under direct observation for at least 4 hours. HR and ECG measurements will be performed according to [Table 5](#) and the subject will be assessed for discharge at 4 hours postdose. Refer to [Section 10.6.7.4](#) for detailed guidance on first-dose cardiac monitoring and subject discharge criteria postdose.

Additional blood sample for PK assessment will be taken 4 hours (\pm 15 minutes) postdose after the Hour 4 ECG.

9.4. Extension Treatment Period

9.4.1. Week 24 Visit

The Week 24 visit will be used to assess eligibility for the Extension Treatment Period and is considered the beginning of the Extension Treatment Period. During this visit, eligibility for

entry into the Extension Treatment Period will be confirmed (ie, meets eligibility criteria; Section 4.3).

At the Week 24 visit, vital signs should be measured first, followed by ECG, predose PK sample collection, study drug dosing at the study site, and first-dose cardiac monitoring (direct observation) for at least 4 hours in all subjects continuing in the Extension Treatment Period. Cardiac monitoring is required because there is a subset of subjects who will transition from placebo in the Double-Blind Treatment Period to an etrasimod dose in the Extension Treatment Period. Refer to Section 10.6.7.4 for detailed guidance on first-dose cardiac monitoring and subject discharge criteria postdose.

9.5. Follow-Up/End of Study

All subjects will have follow-up visits for safety assessment at 2 and 4 weeks after the last dose of study treatment. All AEs should be recorded for 30 days after last dose of study medication (Section 10.6.8.1.9). Refer to Section 10.6.7.2 for details on the post-treatment follow up assessments and procedures for subjects who experience an ongoing AE of decreased lymphocyte count or infection.

In the event that a subject fails to attend any follow-up visits, all reasonable efforts will be made to contact the subject to ensure that he/she is in satisfactory health. All contacts and contact attempts must be documented in the subject's medical record.

9.6. Early Termination

Subjects who discontinue the study prior to the end of the 24-week Double-Blind Treatment Period or the 28-week Extension Treatment Period (Week 52) will return to the study site for an ET Visit. The ET Visit should occur within 7 days of last dose and before initiation of any new treatments.

Site staff will work with subjects who withdraw early to obtain as much follow-up data as possible, including an EGD, if not done within 4 weeks, and PFTs and ophthalmic and OCT testing. If a subject discontinues due to pregnancy, they may not be required to complete the EGD and biopsy.

